Hypothesis 1b: Time periods during which clinics are randomly assigned to receive the modified imaging reports will have a lower rate of subsequent opioid prescriptions than time periods during which clinics do not receive modified reports.

Aim 1c: To determine if inserting epidemiological evidence decreases subsequent cross-sectional imaging magnetic resonance (MR) and computed tomography (CT).

Hypothesis 1c: Time periods during which randomly assigned clinics receive modified imaging reports will have a lower rate of subsequent cross-sectional imaging than time periods for which clinics do not.

Aim 1d: To explore whether adding epidemiological evidence decreases overall costs of care for low back pain based on CMS reimbursement.

Hypothesis 1d: Clinics that are randomly assigned to receive the modified imaging reports will have lower back pain-related estimated payer costs than clinics whose patients do not receive modified reports. Costs are another outcome that are highly relevant to both patients and health systems.

Aim 2: To determine whether inserting age-specific prevalence of imaging findings in asymptomatic subjects has a differential effect on subsequent back-related interventions if inserted into lumbar spine MR and CT imaging reports compared with plain films.

Hypothesis 2: Inserting epidemiological information into plain film reports will result in a greater decrease in subsequent back-related interventions than similar information put into MR and CT reports. Given that plain films are generally obtained earlier in the course of back pain and more frequently than MR and CT, the potential impact of inserting epidemiological information into plain film reports is large.

Aim 3: To determine if specific imaging findings influence subsequent interventions.

Hypothesis 3: Inserting the statement will result in a greater decrease in subsequent interventions for patients without clinically important findings compared with patients who have clinically important imaging findings. Our work and others have shown that certain imaging findings are likely to be clinically more important than others (e.g. nerve root compression, moderate to severe central stenosis, disc extrusions). We expect that patients without these more important findings will have a greater reduction in subsequent interventions.

4. Study Details

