
Aim 3: To determine whether the presence of certain imaging findings influence subsequent interventions

Hypothesis 3: Inserting epidemiological information will result in a greater decrease in subsequent interventions for patients without findings that are clearly clinically important compared with patients who have clinically important imaging findings.

Our work and others have shown that certain imaging findings are likely clinically more important than others (e.g. nerve root compression, moderate to severe central stenosis, disc extrusions). To address this hypothesis, we will use the returned result from radiology to categorize imaging findings into clinically important versus not clinically important. We have identified central canal stenosis, nerve root compression and disc extrusion (a type of herniation) as the clinically most important imaging findings. This is in contrast to findings that are less clinically important (disc bulge, disc narrowing, Modic change, annular fissure, etc).

In each separate analysis of Aim 1 outcomes, we will add an indicator of clinical importance and a clinical importance by treatment interaction term in the model. Similar to Aim 2, primary inference will

again be on the interaction term, where we expect that patients without these more important findings will have a significantly greater reduction in subsequent interventions compared to patients with important findings.

Table 6: Milestones for UH3 (Implementation Phase)- Years 2-5

Year of Project	UH3 Milestone	Comment
Year 2	Final testing of intervention deployment	To be completed before Wave 1 of randomization scheduled for April, 2014
	Intervention implemented at 40% of clinical sites	Planned staggered implementation using stepped wedge design will require close monitoring of progress.
	Algorithm finalized for electronic medical record extraction and tested at all sites	This will continue the work started as UH2 Milestone #4. Each site will require a customized algorithm- hence the need for site-specific development and testing
	Protocol paper submitted for publication	We will prepare a manuscript describing our study protocol and procedures.
Year 3	Randomized intervention implemented at 80% of clinical sites	Planned staggered implementation using stepped wedge design will require close monitoring of progress.

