**Primary Analysis:** The primary longitudinal model for back pain specific RVUs will use a time-varying intervention status indicator  $Status_{kt}$  (0 = control, 1 = intervention, for clinic  $k$  at time  $t$ ). Use of the time-dependent intervention status indicator permits both within-clinic contrasts that inform intervention effects (post-versus pre-intervention) as well as contrasts across clinics with different intervention statuses within each time period. The specific regression model will adopt a functional form given below, with fixed effects for time (linear), age (18-39, 40-59, 60+, using two dummy variables), imaging modality type (plain film, CT, MRI using two dummy variables), and clinic size (small, medium, large, using two dummy variables), and site (Group Health Cooperative, Henry Ford, Kaiser Permanente, Mayo Clinic, using three dummy variables) in addition to random

Lumbar Imaging Reporting with Epidemiology (LIRE)  
 STATISTICAL ANALYSIS PLAN

effects for provider, clinic, and intervention status:

[figure not shown]
$$Y_{ijk} = \beta_0 + \beta_1 \cdot Time_t + \beta_2^T \cdot Age_{ijk} + \beta_3^T \cdot Modality_{ijk} + \beta_4^T \cdot Size_k + \beta_5^T \cdot Site_k + \lambda_0 \cdot Status_{kt} + \quad \text{mean model}$$

$$b_{k,0} + b_{k,1} \cdot Status_{kt} + \quad \text{clinic random effects}$$

$$a_{jk,0} + e_{ijk} \quad \text{provider random effects and errors}$$

We will collect the outcome measure  $Y_{ijk}$  on patient  $i$  ( $i=1,2,\dots,n_j$ ) under primary care provider  $j$  ( $j=1,2,\dots,n_k$ ) enrolled in time period  $t$  ( $t=0,1,2,\dots,5$ ) in order to evaluate the overall effect of the intervention at the level of the clinic  $k$  ( $k=1,2,\dots,110$ ). Note that we will collect a single outcome measure for each subject recording the total utilization (RVU) over the 12 months after the index imaging event. Given that the random effects structure may contain additional elements (see below) we will use a robust standard error to test the null hypothesis that  $\lambda_0 = 0$ . For example, using SAS PROC MIXED we can use the “empirical” option in order to obtain robust standard errors. Alternatively, use of the jackknife (at the clinic level) provides a robust standard error estimate (if using R and *lmer*) that is simple to compute.

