## Lumbar Imaging Reporting with Epidemiology (LIRE) STATISTICAL ANALYSIS PLAN

where  $p_{ijk}$  denotes the probability that  $Y_{ijk}=1$ . Our secondary outcome analysis parallels the primary and will be based on a natural multilevel mixed model, with additional robust secondary analysis provided by GEE. For Aim 1c we will use  $Y_{ijk}=1$  if CT or MR imaging occurs within a specified timeframe (e.g. 90 days or 12 months) after the index imaging event.

**Medical costs (Aim 1d):** Spine-related costs of care will be estimated using two approaches. First, we will use the spine-related RVU calculated in Aim 1a and estimate clinic-level, spine-intervention expenditures using the annual Medicare-determined payment amount per RVU (e.g., CY2013 = \$34.023 per RVU). (reference: <http://www.cms.gov/Outreach-and-Education/Medicare-Learning-Network-LN/MLNProducts/downloads/medcrephyschedfctsht.pdf> )

Second, as a proxy for costs of spine care, we will use a standard set of reimbursement amounts, i.e., CMS-based payments, and estimate clinic-level spine-related aggregate expenditures by applying CPT-based payment amounts to specific spine-intervention events (e.g., imaging, office visits, procedures, other). We will present monthly and annual means, medians, and ranges of clinic-level cost estimates, prior to and subsequent to implementing the epidemiological intervention. We will assess the level of right-skewness in the expenditure estimates and use t-tests to compare arithmetic means for clinic-level expenditures. In the case of considerable skewness, we will test for differences in logarithmically transformed mean clinic-level expenditures (before and after implementing intervention). We will also describe categories of prescriptions ordered, when available in the electronic medical records for a health system, and estimate costs for prescribed spine-related medications

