**Analysis for Aim 2:** The hypothesis of Aim 2 is that there will be a differential effect of the intervention according to the imaging modality used. In order to test this hypothesis we will analyze patient-level data according to the appropriate LMM or GLMM given above, but including the interactions between  $Modality_{ijk}$  indicators (modeled using two indicator variables coding CT and MR, with plain film as the reference) and  $Status_{kt}$ . A test of the interaction terms (2 degree of freedom Wald test) will be used to test the null hypothesis that the effect of the intervention does not vary according the imaging modality.

**Analysis for Aim 3:** The hypothesis of Aim 3 is that there will be a differential effect of the intervention according to the results that are found in the imaging report. We will use an additional variable,  $ImageFinding_{ijk}$ , that takes the value 1 if a significant image finding is present, and 0 otherwise (see detail regarding variable specification in protocol). We will test the null hypothesis that the interaction between  $ImageFinding_{ijk}$  and  $Status_{kt}$  is zero using a Wald test.

[figure not shown]
**Power Calculations:** Our UH2 efforts with respect to sample size and statistical power focused on two key items. First, an important aim of our UH2 Working Group 2 was to obtain an accurate clinic and provider count for each health system. We will now randomize  $n=110$  clinics (1,824 PCPs), which is slightly lower than the  $n=128$  clinics (1,898 PCPs) assumed in our initial project application. However, the majority of the clinics that were dropped were those with only one PCP and therefore would not have contributed much information to the analysis. Second, in our Working Group 3 we sought to develop and characterize a composite RVU summary to be used as the primary outcome measure in this study. In our UH2 project application we discussed statistical power in the context of an important secondary outcome measure, a reduction in subsequent opioid prescription rates. We now present statistical power for the primary outcome measure using data from the BOLD Registry to inform key design parameter estimates.

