**Lumbar Imaging with Reporting of Epidemiology (LIRE) Statistical Analysis Plan Revisions**

The following table includes amendments to our statistical analysis plan (SAP) that we included in statistical models for the manuscript but that we did not specify in our original SAP.

Amendments to Statistical Analysis Plan (SAP)	
Number of clinics	

 
• 110 to 98 clinics
 
	When we wrote the SAP we estimated that we would have 110 clinics participating in the trial. We dropped ten clinics prior to randomization for logistical reasons. We dropped two additional small clinics just after randomization and before the first data submission: one had closed and the other had been subsumed in another clinic.
Covariates	We made all decisions regarding covariates before we began the statistical analysis.
Covariates added	Rationale

 
• Site by time interactions
 
	Allow for differential time trends by site

 
• Gender
 
	Allow for outcome differences by gender (precision)

 
• Charlson Comorbidity Index category
 
	Comorbidity measures are associated with outcomes. We sought greater precision by including this general measure of health.

 
• Prior opioid status (opioid models only)
 
	Allow for differences in outcome between those without and those with prior opioid prescriptions (precision)
Covariates transformed	

 
• Time
 
	The SAP and protocol paper indicated that we would model time linearly as 6-month time period (t = 0, 1, 2, 3, 4, 5). Upon further thought, we decided that a more granular measure (i.e. day) would be more appropriate.

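### The planned Aim 3 term is a valid subgroup contrast, but with modality only as a main effect it cannot separate findings from modality; a parallel model with Modality-by-Status would be a cheap addition (minor)

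*Protocol*

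**What the plan says.** Aim 3 in Protocol 5.7 is headed "To determine whether the presence of certain imaging findings influence subsequent interventions". Hypothesis 3 in Protocol section 3 is a comparison of patient groups: "We expect that patients without these more important findings will have a greater reduction in subsequent interventions". To test it, Protocol 5.7 says that in each Aim 1 analysis "we will add an indicator of clinical importance and a clinical importance by treatment interaction term in the model". The SAP (Analysis for Aim 3) defines an indicator "that takes the value 1 if a significant image finding is present, and 0 otherwise" and tests its interaction with intervention status by a Wald test.

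Modality is a covariate in the models being extended. The SAP's primary model lists "imaging modality type (plain film, CT, MRI using two dummy variables" among its fixed effects. The logistic model for opioids has the same mean structure, and the cross-sectional imaging analysis follows it. Protocol 5.7 also adjusts for image type under Aims 1a and 1c. Modality-by-Status appears only under Aim 2: "A test of the interaction terms (2 degree of freedom Wald test) will be used to test the null hypothesis".

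The SAP revisions replace the binary finding indicator with three categories: likely important findings, only findings named in the inserted text, and neither. The one interaction they add among covariates is site by time, with the rationale "Allow for differential time trends by site". Modality-by-Status is not added. Aim 1d is outside this point, because there the SAP will "use t-tests to compare arithmetic means for clinic-level expenditures".

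**The concern.** A modality main effect adjusts the level of the outcome, not the size of the intervention effect. Randomisation protects the comparison of intervention with control; it does not make imaging findings independent of modality. If both the intervention effect and the frequency of important findings differ by modality, patients with and without findings differ in intervention effect partly because they were imaged differently.

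The plan supplies the first condition, since differential effect by modality is Aim 2. A significant Aim 3 result could then be read as showing that the text works better when nothing important is found, when it partly shows that the text works better on one modality. A null result could hide a finding effect that a modality effect offsets.

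The direction cannot be fixed in advance, because Protocol 5.7 gives two expectations for Aim 2. Hypothesis 2 expects a greater decrease with plain film, which would add to the Hypothesis 3 contrast. The analysis paragraph below it expects a greater reduction with advanced imaging, which would subtract from it.

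**Working it through.** The documents state no power or error rate for Aim 3, so there is no figure of theirs to reproduce.

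**Inputs from the documents:** about 100,000 patients (Protocol section 7, before 7.2); residual variance 1.230 and clinic variance 0.026 on log(RVU+1) (SAP, Power for Primary Outcome); 98 clinics (SAP revisions); five waves over six periods, so the share of periods on intervention is (5+4+3+2+1)/30 = 0.50.

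**Assumed inputs (not in the documents):** plain film 60-80% of index images; important findings on 20-40% of MR/CT and 0-5% of plain films.

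**Carry-over.** With Status unrelated to modality and findings, the planned coefficient equals

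within-modality finding effect + D × [P(MR/CT | finding) − P(MR/CT | no finding)],

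where D is the difference in intervention effect between MR/CT and plain film.

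*Worked case:* MR/CT 30%, findings on 30% of MR/CT and 2% of plain films.
- P(finding) = 0.3×0.30 + 0.7×0.02 = 0.104
- P(MR/CT | finding) = 0.090/0.104 = 0.865
- P(MR/CT | no finding) = 0.210/0.896 = 0.234
- Carry-over = 0.865 − 0.234 = 0.631

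If findings are equally frequent on both modalities, the bracket is zero.

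**Rejection with no finding effect within modality.**
- Standard error = √[1.23/(100,000×0.25×0.104×0.896)] = 0.0230
- D = 0.05: shift 0.0316, z = 1.37, rejection 28%
- D = 0.025: shift 0.0158, z = 0.69, rejection 11%
- D = 0.01: shift 0.0063, z = 0.27, rejection 6%

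The 5% reduction used for primary power is −ln(0.95) = 0.051 on the log scale, so D = 0.05 means a modality difference about as large as that whole effect.

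| | Binary finding, 1 df | Three categories, 2 df |
|---|---|---|
| Carry-over | 33-87% (median 63%) | 28-97% (important versus neither) |
| Rejection, D = 0.01 | 5-7% | 5-7% |
| Rejection, D = 0.025 | 6-15% (median 10%) | 6-19% (median 9%) |
| Rejection, D = 0.05 | 10-46% (median 24%) | 8-62% (median 24%) |

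The three-category column also assumes text-only findings on 30-50% of MR/CT and 20-50% of plain films. On a wider grid for the binary version (plain film 40-90%, findings on 10-50% of MR/CT and 0-20% of plain films, always higher on MR/CT), carry-over is 3-95% and rejection at D = 0.05 is 5-57%.

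**Opioid outcome.** The SAP's 22% rate and 7.5% reduction give 0.22×0.925 = 20.35%, a logit difference of 0.099. For the binary version, rejection is 9-39% if the modality difference equals that whole effect, 6-14% at half of it and 5-7% at a quarter.

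**With Modality-by-Status added.** Carry-over is zero and rejection is 5% throughout the grid. In the worked case the variance of the finding indicator falls from 0.104×0.896 = 0.0932 to 0.3×0.21 + 0.7×0.0196 = 0.0767, so the standard error grows by √(0.0932/0.0767) = 1.10.

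**Check with clustering.** Simulation with the worked-case inputs and binary finding: 98 unequal clinics, five waves, clinic variance 0.026, assumed SD 0.03 for the clinic intervention effect, clinic-robust Wald test, 1,000 replicates.

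| Scenario | Planned term rejects | With Modality-by-Status |
|---|---|---|
| No finding effect, D = 0 | 6% | 5% |
| No finding effect, D = 0.025 | 12% | 6% |
| No finding effect, D = 0.05 | 30% | 7% |
| Finding effect 0.05, D = 0 | 60% | 53% |
| Finding effect 0.05, opposing D of 0.05 | 15% | 52% |

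**The case against.** The strongest reply is that the plan estimates what it says it will test. Hypothesis 3, the SAP's Aim 3 paragraph and the three-category revision all describe a comparison of intervention effects between patient groups. No passage promises an effect of findings net of modality; only the verb in the aim's heading suggests it. This stands. A reader might infer from the rejection rates that the Aim 3 test has an inflated type I error. It does not: the rates are not errors for the marginal contrast. They show how often that contrast would be significant when findings have no effect within modality.

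The size also rests on assumptions. Modality mix, finding rates by modality and the modality effect are all undocumented, and two conditions must hold together. That stands too, and it is why the ranges are wide. The binary indicator has been superseded, so the binary figures illustrate the mechanism; the three-category column is closer to the current analysis.

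A reader might further infer that a finding effect surviving adjustment for modality could be attributed to the findings. The documents do not support this. The inserted text is tailored by age as well as modality (Protocol 5.6), and in the protocol's Table 3 moderate or severe stenosis rises from 7% under 45 to 21% over 65 in people without back pain. Age, too, is only a main effect.

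Aim 2 will report whether modality modifies the effect, which helps. It does not show how much of the Aim 3 contrast remains once that is allowed for. The SAP's call for an additional variable, directly after the Aim 2 paragraph, might be read as building on the Aim 2 model, but the protocol ties Aim 3 to the Aim 1 analyses.

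**Conclusion.** The point holds as a minor, cheap improvement to the Aim 3 analyses of RVUs, opioid prescriptions and cross-sectional imaging. The planned contrast alone cannot show whether findings or modality drive a difference. The consequence runs from almost none to substantial. It vanishes if the intervention effect is the same across modalities or if findings are equally frequent on each. It becomes material only when findings are concentrated on MR/CT and the modality difference approaches the whole effect used for primary power. Confidence is high on the model terms and the algebra, and low on where the trial falls in the range. Nothing here touches the primary Aim 1 analysis or the validity of the Hypothesis 3 subgroup contrast.

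**What to change.** 1. Keep the planned Finding-by-Status contrast as the Aim 3 result and describe it as a marginal subgroup contrast.
2. For Aims 1a-1c, prespecify beside it the same model with Modality-by-Status added, using the three-category finding variable. Report both estimates with confidence intervals. If they differ materially, state that the Aim 3 difference partly reflects modality.
3. Do not make the second model a significance gate or a licence for causal attribution to findings. Age-by-Status can be added to the same sensitivity model. An MR/CT-only run is optional support.
4. Separately, reconcile the two opposite expectations for Aim 2 in Protocol 5.7.

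The data are already being collected, and the planned test and its power do not change. The price is precision in the second estimate: its standard error is about 3-24% larger in the binary version and 2-39% larger for important versus neither in the three-category version. For a finding effect of 0.05 and no modality difference, binary power is 29-80% for the planned term, 25-71% with Modality-by-Status and 25-60% for MR/CT only. This is a further reason to read the second model by its interval rather than by its p-value.

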7.2 Research Data

Research data will consist of individual subjects' medical record data and information on clinics and providers. We will collect all data passively with automated data extractions. Data extracted from the medical record will include demographic data, variables related to imaging, pharmacy, procedures, hospitalizations, and other factors related to healthcare utilization. We will not collect patient reported outcomes unless they are part of the medical record.

We will collect demographic data on primary care providers and will code the data in such a way that an individual practitioner is not identifiable. We will use patient data to derive pre and post randomization rates of spine related interventions (diagnostic imaging, opioid prescriptions, spine related procedures, physical therapy etc.) among a provider's patient panel.

We will code with a unique study identification number, without reference to patient or provider identity. The code key will be kept secured at the recruitment site, separate from the data. Only the site researchers will have access to the code key (not the researchers at the DCC).

